#### 1. BACKGROUND AND RATIONALE

#### 1.1 General Introduction

*Panax notoginseng* (Burk.) F.H. Chen (*Panax notoginseng*) is a species of the genus *Panax*, family *Araliaceae*. Three species in this genus (*Panax ginseng* C.A. Meyer, *Panax quinquefolius* L. and *Panax notoginseng* (Burk.) F.H. Chen) are highly regarded as medicinal plants in China and the USA (Wen and Zimmer, 1996). *Panax notoginseng* belongs to the same genus as Korean ginseng (*Panax ginseng* Meyer) and American ginseng (*Panax quinquefolius* L.), and their main components are similar (Li et al., 2014). The root of *Panax notoginseng*, known as Sanqi or Tianqi in East Asian countries, is one of the primary herbs in traditional Chinese medicine. Sanqi, which has been widely used as a tonic and haemostatic drug for more than 400 years, still has an important place in today's regional market. With the increasing study of Chinese material medica, substantial efforts have been made to research the phytochemistry and pharmacological effects of *Panax notoginseng*, and a variety of pharmacological effects have been found.

Typical botanical characteristics of *Panax notoginseng* include growing to a height of 30-60 cm, dark green leaves branching from a stem and a cluster of red berries in the middle. The stems are upright, simple, erect and unbranched (Guo et al., 2010). The main root is conical or cylindrical and ranges in length from 1 to 6 cm. The main root is taupe or drab yellow on the surface, with several wrinkles and root marks. Generally, *Panax notoginseng* is removed from the soil and dried before it blooms in autumn. It can be ground singly into powder that is swallowed or combined with other herbs (Committee for the Pharmacopoeia of China, 2010). The distribution of *Panax notoginseng* is very narrow due to its sensitivity to sunlight. After a long period of evolution, it grows primarily in the Wenshan mountain area of Yunnan province. It has a narrow habitat located around N 23.5° and E 104° that ranges in altitude from 1200 to 2000 m. A large percentage of the raw materials in China is produced here (Guo et al., 2010).

As for Ethnopharmacology, the root of *Panax notoginseng* has played an indispensable role in Chinese healthcare for a long time. It is the main ingredient in Yun Nan Bai Yao (雲南白藥), a famous haemostatic herbal remedy that is used to stop bleeding, decrease inflammation and relieve pain (Sun et al., 2010). *Panax notoginseng* is also one of the sources of cardiotonic pill that has been used in China, Korean and Russia for the treatment of cardiovascular diseases, such as occlusive vasculitis, coronary diseases, atherosclerosis, and cerebral infarction (Zhao et al., 2006). The initial description of this plant can be traced back to the Compendium of

Material Medica (《本草綱目》), written by Shi Zhen Li. In this classic book, Panax *notoginseng* was recorded to have the actions to stop bleeding, remove blood stasis, alleviate pain, and it could be applied to treat bleeding caused by swords or axes, as well as hemoptysis, hematemesis, epistaxis and blood dysentery. Then the subsequent book Supplements for Compendium of Material Medica(《本草綱目拾遺》), written by Xue Min Zhao, described the function of Sangi as similar to that of Panax ginseng C. A. Meyer. The difference is that *Panax ginseng* C.A. Meyer is good for tonifying qi (氣), while Panax notoginseng is especially helpful for nourishing the blood. It is worthy to note that this tonic action, which is usually used in folk hasn't been written in Compendium of Material Medica(《本草綱目》) and many material medical books, and just can be found in few books, like New Compilation of Material Medica (《本草新编》) and Chinese Medicine Dictionary (《中國醫藥大辭典》). In the Chinese pharmacopoeia, the properties of this herb are described as warm in nature, sweet and slightly bitter in taste. It is attributive to the liver and spleen meridians, it has the actions to dissipate blood stasis, stop bleeding, promote blood circulation and alleviate pain, so it can be applied in haemoptysis, hematemesis, rhinorrhagia, haemafecia, metrorrhagia and metrostaxis, traumatic bleeding and pain caused by traumatic injury (Committee for the Pharmacopoeia of China, 2010).

Because of its defined clinical effects, some formulas were created by ancient doctors. Nowadays, many prescriptions are in clinical use. There are nearly 60 kinds of Chinese patent medicines in the Chinese pharmacopoeia, and the forms including capsules, granules, tablets, pills, dripping pills, powders, etc., in which capsules and tablets are the most used forms (Shi et al., 2012). Although *Panax notoginseng* have been used massively, there are over 1500 t of stems and leaves of *Panax notoginseng* were turned out every year, but less than 5% stems and leaves is to be used only.

The stems of *Panax notoginseng* and the leaves of *Panax notoginseng* demonstrate a certainty of clinical application of anti-tumor activity (Jiang et al., 2014). The compositions and contents of saponins isolated from the leaves of *Panax notoginseng* are significantly different from the underground parts in that the leaves and stems of *Panax notoginseng*, mainly contain plentiful PPD-type saponins, such as ginsenosides Rb3, Rb1, Rc, and notoginsenoside Fc (Wang et al., 2016). Furthermore, chemical profile indicates the leaves of *Panax notoginseng* contain the marker saponins F2, 20(R)-Rg3, 20(S)-Rg3, and Rh2 (Wang et al., 2016), and these compounds illustrate anti-proliferation effect on human colorectal cancer cells (Wang et al., 2007).

In a myelosuppression attenuation study using DS1370 (same as drug substance DS-1370 used in this study), dry extracts of *Panax notoginseng* powder, 30 mice were divided into 5 groups, which were control group, docetaxel (Doc) + cisplatin (CP) group, Doc + CP + DS1370 (1,072 mg/kg) group, Doc + CP + DS1370 (536 mg/kg) group, Doc + CP + DS1370 (268 mg/kg) group. Each groups included 6 mice. Doc (12 mg/kg) was injected to mice via intraperitoneal injection on Day 0, then, CP (12 mg/kg) was injected to mice via intraperitoneal injection 6 hours later, and sample DS1370 was administered by oral gavage from Day 1 to Day 5. The study results indicate sample DS1370 can attenuate the myelosuppression that caused by cisplatin and docetaxel injection. According to the results of peripheral blood cells count and bone marrow hematopoiesis ability, the effective doses of DS1370 are 536 mg/kg and 1072 mg/kg. Additionally, the dosages of DS1370 at 268, 536, and 1072 mg/kg are considered to be safe with employed chemotherapy as these dosages after chemotherapy did not cause further body weight reduction or tumor suppression on mice.

#### 1.2 Rationale and Justification for the Study

1.2.1 Rationale for the Study Purpose

*Panax notoginseng* has recently attracted pharmaceutical attention for its potential effects to treat myelosuppression. This phase I study is therefore proposed to evaluate the safety and tolerability profiles of Careseng 1370 as single agent in healthy volunteers as reference to determine recommended dose to treat myelosuppression for cancer subjects receiving chemotherapy in the future.

## 1.2.2 Rationale for Doses Selected

Based on the preclinical toxicity study, no-observed-adverse-effect level (NOAEL) of DS-1370 is determined as 675 mg/kg/day in rats of both genders, leading to human equivalent dose (HED) of 675/6.2 = 108.8 mg/kg/day. Considering choosing a safety factor of 10, the maximum recommended starting dose (MRSD) is 10.88 mg/kg/day, equivalent to around 653 mg/day for a 60-kg adult. The pharmacology data indicates that administration of DS-1370 536 mg/kg and 1,072 mg/kg (but not 268 mg/kg) daily are efficacious in treating myelosuppression caused by docetaxel and cisplatin in mice. The HED (divided by 12.3) based on 536 mg/kg is 43.58 mg/kg/day (2,614.63 mg/day for a 60-kg adult). Each Careseng 1370 sachet will be around 4,000 mg in weight containing powder of 652 mg DS-1370 (16.3% w/w) plus 3,348 mg of excipients (83.7% w/w). The MRSD will be one sachet per day and the anticipated therapeutic dose (ATD) range will be 4 to 8 sachets per day. One, two, and three sachets of Careseng 1370 per day (level A, B, and C) are therefore selected at Sponsor's discretion for this study. Consideration of

unexpected drug effects on human body, one modified cohort (level D) is planned as the lower dose level below the starting dose level A. The modified cohort (level D) will be implemented when the dose de-escalates from level A.

#### 1.2.3 Rationale for Study Population

Healthy volunteers are recruited to explore the safety and tolerability profiles of Careseng 1370 for safety concern and as reference to determine recommended dose for cancer subjects receiving chemotherapy in the future.

1.2.4 Rationale for Study Design

Single arm, dose escalation of Careseng 1370 with traditional 3+3 paradigm will be employed to achieve the purpose of this study.

#### 1.3 **Potential Risks and Benefits**

There will be no potential benefits for healthy volunteers to participate in this study.

Potential risks of Careseng 1370 are based on the toxicology findings in Sprague-Dawley (SD) rats. Possible influence on coagulation prolonged prothrombin time (PT) and activated partial thromboplastin time (APTT) was noted in both sexes of rats receiving mid- (1,350 mg/kg/day) and high-dose (2,700 mg/kg/day) for 13 weeks. But the prolonged PT and APTT were not seen at the end of recovery period in 2,700 mg/kg recovery animals. It was also noted that the mean body weights of mid- and high-dose male rats were 9.3% and 13.8% lower than that of the controls, respectively. Final mean body weight of high-dose recovery male rats was 11.8% lower than that of the controls. Final mean body weight gains of mid- and high-dose male rats were 15.7% and 23.2% lower than that of the controls. Final mean body weight gains of high-dose recovery males was 19.2% lower than that of the controls. Therefore, body weight loss and bleeding prolonged are possible risks that subjects in this study may experience.

#### 2. OBJECTIVES AND ENDPOINTS

#### 2.1 Objectives

#### **Primary objective:**

The primary study objective is to explore the safety and tolerability profiles of Careseng 1370 as single agent based on DLT observed in healthy volunteers. The results will be employed for future study to determine the MTD of Careseng 1370 to treat chemotherapy-induced myelosuppression in advanced non-small cell lung cancer (NSCLC) patients.

DLT is defined as any  $\geq$  Grade 2 adverse event from Day 1 to Day 10 (DLT observation period), causally at least possibly related to Careseng 1370 administration as judged by the investigator. The grading system applied in this study is "Guidance for Industry: Toxicity Grading Scale for Healthy Adult and Adolescent Volunteers Enrolled in Preventive Vaccine Clinical Trials" (Appendix 1), issued by United States Food and Drug Administration in September 2007. The definition of Grade 5 (death) was added to this grading system as it was not defined in the guidance (Section 8.2 and Appendix 1).

#### Secondary objective:

The secondary study objective is to evaluate the pharmacokinetic (PK) profiles of marker ingredient in Careseng 1370, 20(S)-protopanaxadiol (PPD), and its metabolites in healthy volunteers.

#### 2.2 Endpoints

2.2.1. Primary endpoints

Incidence of adverse events (AEs) and serious adverse events (SAEs)

- 2.2.2. Secondary endpoints
  - Changes from baseline to applicable post-dosing visits in vital signs, physical examination, body weight, EKG and laboratory examination results. Baseline will be the value of measurement closest to and before start of IP administration.
  - 2. Pharmacokinetic parameters of marker ingredient in Careseng 1370, 20(S)protopanaxadiol (PPD) and its metabolites
- 2.2.3. Exploratory endpoints

Exploratory endpoints in item 1 below are measured to explore the immunity

1. Change in lymphocyte activity (based on CD3, CD4, CD8, CD19, CD16 and CD56 assessments, presented as CD3+, CD3+/CD4+, CD3+/CD8+, CD19+, CD16+/CD56+, and CD4/CD8 ratio) on Day2, Day 6 and Day 22 compared to the baseline

#### **3.** STUDY POPULATION

#### 3.1 Volunteers Enrollment

In design of traditional 3+3 paradigm with four candidate dose levels, the number of evaluable healthy volunteers will be up to 24.

Note: A volunteer is considered evaluable if he/she

1. receives any Careseng 1370, and

2. experiences DLT OR completes DLT observation period with at least 80% of study drug compliance and has exposed to Careseng 1370 for at least 4 days (level A, B, and C), OR completes DLT observation period with 100% of study drug compliance (level D).

#### 3.2 Inclusion Criteria

A healthy volunteer is eligible for the study if all of the followings apply:

- 1. Adult aged between 20-40 years old (inclusive)
- 2. Physically and mentally healthy volunteer as confirmed by an interview, medical history, clinical examination, chest X-rays, and electrocardiogram. Volunteer with non-clinically significant signs or symptoms may be eligible at investigator's discretion.
- 3. Body Mass Index (BMI) between 18.5 and 24, inclusive (BMI will be calculated as weight in kilogram [kg]/(height in meters) [m^2])
- 4. Clinically normal hematology, biochemistry and urinalysis determinations based on investigator's discretion. Volunteer with non-clinically significant signs or symptoms may be eligible at investigator's discretion.
- 5. Volunteer is willing and able to comply with study procedures and sign informed consent prior to initiation of any study-mandated procedures.

#### **3.3** Exclusion Criteria

Any volunteer meeting any of the exclusion criteria will be excluded from study participation:

1. Volunteer who has a history or evidence of a medical condition that would expose them to a risk of a significant adverse event or interfere with the assessments of safety or pharmacodynamics variables during the course of the trial, including but not limited to hepatic, renal, respiratory, cardiovascular, endocrine, immune, neurological, musculoskeletal or hematological disease as determined by the clinical judgment of the investigator

- 2. Volunteer has received any other investigational agent within 4 weeks prior to the first dose of study drug
- Volunteer has taken or potentially takes any herbal medication/supplements/medicinal food, prescription medication and/or over-thecounter medication within 2 weeks prior to the first dose of study drug
- 4. Volunteer has consumed alcohol, caffeine, grapefruit juice, nicotine, phosphorous supplement, calcium supplement, or food rich in calcium within 24 hours prior to the first dose of study drug
- 5. Female volunteer of childbearing potential who:
  - is lactating; or
  - has positive pregnancy test result at eligibility checking; or
  - refuses to adopt at least two forms of birth control (at least one of which must be a barrier method) from Screening visit to Final visit.

Note: Acceptable forms include:

- 1. Established use of oral, injected or implanted hormonal methods of contraception.
- 2. Placement of an intrauterine device (IUD) or intrauterine system (IUS).
- 3. Barrier methods of contraception: Condom OR Occlusive cap (diaphragm or cervical/vault caps)
- 6. Male volunteer with female spouse/partners who are of childbearing potential refuses to adopt at least two forms of birth control (at least one of which must be a barrier method) from Screening visit until Final visit
- 7. Known or suspected allergy or hypersensitivity to any ingredients of study product
- 8. With history of stroke, myocardial infarction, or Coronary Artery Bypass Graft (CABG) surgery within the last 6 months prior to the screening visit
- 9. With history of cardiac failure (New York Heart Association class 2 or above), unstable angina, or life-threatening arrhythmia within the last 6 months prior to the screening visit
- With blood pressures as systolic blood pressure < 90 mmHg or > 170 mmHg or diastolic blood pressure < 50 mmHg or > 120 mmHg at eligibility checking
- 11. History of psychiatric disorder
- 12. History of left ventricular outflow obstruction, such as aortic stenosis and hypertrophic cardiomyopathy

- 13. With a history of human immunodeficiency virus (HIV) infection or hepatitis B or C infection
- 14. Plan to receive surgery from Screening visit until Final visit
- Known or suspected hypersensitivity to any component of Careseng 1370, including components in plants of *genus Panax*, Tween 80, Kolliphor® P188, Fujicalin, and ginseng flavor

## 3.4 Withdrawal Criteria

Healthy volunteers may be withdrawn from the trial due to any of the following conditions:

- 1. Volunteer decides to withdraw his/her informed consent.
- 2. Volunteer experiences intolerable symptoms.
- 3. Any pathological event, clinical adverse event, or any change in the volunteer's status giving indication to the investigator that further participation in the study may be harmful to the volunteer's health.
- 4. Volunteer becomes pregnant from Screening visit until Final visit. Volunteer's pregnancy status should be checked by serum or urine pregnancy test at Screening visit and Final visit and any time if investigator or volunteer suspects the volunteer is pregnant.
- 5. Volunteer develops DLT.
- 6. Volunteer is lost to follow-up or dies.
- 7. Volunteer misses dosing and fails to reach 80% of study drug compliance, does not keep appointments, or otherwise does not adhere to protocol requirements.

The reasons for withdrawal must be recorded in the electronic Case Report Form (eCRF) and in the volunteer's medical records for all early terminated cases. All study participants withdrawn from the study will be requested as possible to return for assessments scheduled at Final visit. If a volunteer is withdrawn due to an AE, every effort will be made to follow the event until the AE resolved or stabilized at a level acceptable to the investigator.

## 3.5 Concomitant Therapy

All medications, supplements, and herbal medicinal food taken by the study volunteer beginning four weeks prior to the Screening visit up to Final visit will be recorded on the appropriate page of the eCRF. This record will include the name of the medication,

frequency, unit dose, dates of the drug was started and stopped, and the indication for the use of the drug.

Prohibited therapies include the following:

- 1. Other investigational drugs within 4 weeks prior to Day 1 until Final visit
- 2. Other herbal medications/supplements/medicinal food within 2 weeks prior to Day 1 until Day 15
- Prescription medication and/or over-the-counter medication within 2 weeks prior to Day 1 until Day 15
- 4. Alcohol, caffeine, grapefruit juice, nicotine, calcium or phosphorous supplement within 24 hours prior to Day 1 until Day 7
- 5. Food rich in calcium within 24 hours prior to Day 1 until Day 7, including dairy food, soymilk, tofu, black bean, clams, sardines, squid, cauliflower, kale, cabbage, Chinese mustard, basil, black sesame, seaweed, black jelly ear, calcium-fortified food, etc. A calcium-restricted diet plan designed for 4 different dose cohorts (Dose level A: 1,730 mg calcium/day; Dose level B: 960 mg calcium/day; Dose level C: 200 mg calcium/day, Dose level D: 1,730 mg calcium/day) will be provided to volunteers as a dietary guideline during this period of time
- 6. Any type of surgery from Screening visit until Final visit.

Additionally, volunteers will be advised to avoid ingesting excessive amount of food very rich in phosphorous during the dosing period, including yolk, animal organs, dried meat, dried seafood, grains, beans, nuts, royal jelly, coke, beer, yakult, chips, powder of milk, yeast, tea, or cocoa, etc.

Confidential Version: 5.0 Date: 18Sep2020

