## Follow-up visits:

- Day 6: post-dose PK blood sampling for 24 hours, discharge from hospitalization
- Day 7: post-dose PK blood sampling for 48 hours
- Day 8: post-dose PK blood sampling for 72 hours
- Day 12 (±2)

*Note: The definition of "post-dose PK blood sampling" means blood collection for PK after the 1st dose on Day 5.* 

Final visit: Day 22 (±2) or within 3 days after withdrawal is confirmed

Volunteers Inclusion A healthy volunteer is eligible for the study if all of the followings		
Criteria	apply:	
	1. Adult aged between 20-40 years old (inclusive)	
	2. Physically and mentally healthy volunteer as confirmed by an interview, medical history, clinical examination, chest X-rays, and electrocardiogram. Volunteer with non-clinically significant signs or symptoms may be eligible at investigator's discretion.	
	3. Body Mass Index (BMI) between 18.5 and 24, inclusive (BMI will be calculated as weight in kilogram [kg]/(height in meters)  [m  ])	
	4. Clinically normal hematology, biochemistry and urinalysis determinations based on investigator's discretion. Volunteer with non-clinically significant signs or symptoms may be eligible at investigator's discretion.	
	5. Volunteer is willing and able to comply with study procedures and sign informed consent prior to initiation of any study-mandated procedures.	
Volunteers Exclusion Criteria	Any volunteer meeting any of the exclusion criteria will be excluded from study participation:	
	1. Volunteer who has a history or evidence of a medical condition that would expose them to a risk of a significant adverse event or interfere with the assessments of safety or pharmacodynamics variables during the course of the trial, including but not limited to hepatic, renal, respiratory, cardiovascular, endocrine, immune, neurological, musculoskeletal or hematological disease as determined by the clinical judgment of the investigator	
	2. Volunteer has received any other investigational agent within 4 weeks prior to the first dose of study drug	
	3. Volunteer has taken or potentially takes any herbal medication/supplements/medicinal food, prescription medication and/or over-the-counter medication within 2 weeks prior to the first	

dose of study drug

- 4. Volunteer has consumed alcohol, caffeine, grapefruit juice, nicotine, phosphorous supplement, calcium supplement, or food rich in calcium within 24 hours prior to the first dose of study drug

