- Maximum Tolerated Dose (MTD)-Evaluable Population:
 - 1. A subset of ITT population
 - 2. Experiences DLT OR with at least 80% of study drug compliance and has exposed to Careseng 1370 for at least 4 days

(4) For Visit Name (in Tables and Figures) and Visit Code (in Subject Data Listing):

Visit No.	Visit Description	Visit Day	Visit Name	Visit Code
1	Visit 1 Screening Visit	-14 ∼ -1	Visit 1 (Screening)	V01
2	Visit 2 Hospitalization: Day -1 to Day 1	1	Visit 2 (Day 1)	V02D01
3	Visit 3 Discharge: Day 2	2	Visit 3 (Day 2)	V03D02
4	Visit 4: Day 3	3	Visit 4 (Day 3)	V04D03
5	Visit 5: Day 4	4	Visit 5 (Day 4)	V05D04
6	Visit 6 Hospitalization: Day 4 to Day 5	5	Visit 6 (Day 5)	V06D05
7	Visit 7 Discharge: Day 6 (24±2 hrs post-last dose)	6	Visit 7 (Day 6)	V07D06
8	Visit 8 Follow-up Visit: Day 7 (48±2 hrs post-last dose)	7	Visit 8 (Day 7)	V08D07
9	Visit 9 Follow-up Visit: Day 8 (72±2 hrs post-last dose)	8	Visit 9 (Day 8)	V09D08
10	Visit 10 Follow-up Visit: Day 12±2	10 ~ 14	Visit 10 (Day 12)	V10D12
11	Visit 11 Final Visit (Day 22±2, within 3 days after withdrawal)	22	Visit 11 (Day 22)	V11D22
-	Unscheduled Visit	-	-	V□□.□

(5) Full term for 'Protocol Deviation Code':

Code	Full Term
<to added="" be="" data="" final="" in="" real="" tabulation="" upon=""></to>	

(6) For clinical relevance

CS: abnormal and clinically significant LLN: lower limit of normal range NCS: abnormal but not clinically significant ULN: upper limit of normal range

(7) For Transition of Clinical Relevance

Relieved CS (Medical History or Adverse Event) at baseline to Normal / NCS at

visit.

Unchanged Including Normal at baseline to NCS at visit, NCS at baseline to Normal

at visit.

Worsened (Medical History) Normal / NCS at baseline to CS (Medical History) at visit

Worsened (Adverse Event) Normal / NCS / CS (Medical History) at baseline to CS (Adverse Event)

at visit

Version 1.0, 08-SEP-2022 Confidential
Protocol No.: Careseng 1370-01 Page 6 of 20 A2 Healthcare Taiwan Co.

Careseng 1370 for Healthy Volunteers

(8) Abbreviations of statistics

N: number of non-missing values Missing: number of missing values

Mean: mean of values

SD: standard deviation of values Q1: 25% quartile of values Q3: 75% quartile of values

Median: median of values

IQR: inter-quartile-range (IQR=Q3-Q1)

Min: minimum of values Max: maximum of values CI: confidence interval

Version 1.0, 08-SEP-2022 C Protocol No.: Careseng 1370-01 P

Careseng 1370 for Healthy Volunteers

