14.3 SAFETY DATA

Visit 11 is final visit or early withdrawal visit.

Safety data below except for visit 8 and visit 9 not in its visit window will be shifted to corresponding scheduled visit for analysis as in table below. If there is any data shifting, visit name will be presented as 'Adjusted Visit' for the visits reallocated to its original scheduled visit or the next visit after preceding scheduled visit.

Adjusted Visit	Laboratory Assessment†	Physical Examination	Body Weight	Vital Signs	12-Lead Electrocardiogram
Baseline	N Baseline is Visit 1 (Screening), no need to present statistics for Baseline additionally	N.	Y Baseline is Day 1, or alternatively as Visit 1 if Day 1 data are not available.	Y Baseline is Day 1 Pre-dose, or alternatively as Visit 1 if Day 1 Pre-dose data are not available.	Y Baseline is Day 1 Predose, or alternatively as Visit 1 if Day 1 Predose data are not available.
• Visit 1	Y	Y	Y	Y	Y
• Visit 2 (Day 1)	Y (8 hours post-first dose)	Y (Pre-dose), (8 hours post- first dose)	Y	Y (Pre-dose), (1 hour post-first dose), (4 hours post-first dose), (8 hours post-first dose)	Y (Pre-dose), (1 hour post-first dose), (4 hours post-first dose), (8 hours post-first dose), (12 hours post-first dose)
• Visit 3 (Day 2)	Y	Y	Y	Y	Y (Pre-dose), (1 hour post-first dosing post-first dosing)
• Visit 4 (Day 3)	Y	Y	Y	Y	Y (Pre-dose), (1 hour post-first dosing)
• Visit 5 (Day 4)	Y	Y	Y	Y	Y (Pre-dose), (1 hour post-first dosing)
• Visit 6 (Day 5)	Y (Pre-dose), (4 hours post dosing)	Y (Pre-dose), (4 hours post dosing)	Y	Y (Pre-dose), (4 hours post dosing)	Y (Pre-dose), (1 hour post-first dose), (4 hours post-first dose), (8 hours post-first dose), (12 hours post-first dose)
• Visit 7 (Day 6)	Y	Y	Y	Y	Y
• Visit 8 (Day 7)	N	N	N	N	N
• Visit 9 (Day 8)	N	N	N	N	N
• Visit 10 (Day 12)	Y	Y	Y	Y	Y
• Visit 11 (Day 22)	Y	Y	Y	Y	Y

Y denotes that the Visit is performed in the corresponding tables.

N denotes that the Visit is not performed in the corresponding tables.

[†] Visit 1, 3, 7, 11 only for immunology

Careseng 1370 for Healthy Volunteers

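### Late vital signs and EKG (Visits 10 and 11) are compared with a baseline taken after 24 hours without alcohol, caffeine or nicotine, but no such condition applies at those visits.

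*Protocol*

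**What the plan says.** - **Restriction.** Protocol section 3.5, item 4: "Alcohol, caffeine, grapefruit juice, nicotine, calcium or phosphorous supplement within 24 hours prior to Day 1 until Day 7". Items 2 and 3 of the same list (herbal products and medicines) run to Day 15.
- **Entry condition.** Protocol section 3.3, criterion 4 excludes anyone of whom it is true that "Volunteer has consumed alcohol, caffeine, grapefruit juice, nicotine" (or the listed calcium and phosphorus sources) in the 24 hours before the first dose. No criterion excludes habitual users.
- **Baseline.** Protocol section 2.2: "Baseline will be the value of measurement closest to and before start of IP administration". For vital signs, the visit table in SAP section 14.3 says "Baseline is Day 1 Pre-dose, or alternatively as Visit 1 if Day 1 Pre-dose data are not available". The EKG rule there, repeated in SAP section 14.3.8, is the same. The laboratory baseline is different: it is Visit 1 (Screening).
- **Late assessments.** Protocol section 7 schedules vital signs and EKG at Visits 10 and 11. The SAP visit list places them at "Visit 10 Follow-up Visit: Day 12±2" and "Visit 11 Final Visit (Day 22±2, within 3 days after withdrawal". SAP section 14.3 tabulates both visits against baseline, and the continuous layout includes a 95% confidence interval for the change.
- **DLT window.** Protocol section 2.1 counts a qualifying "adverse event from Day 1 to Day 10 (DLT observation period").
- **Fasting.** Protocol section 7 asks for fasting at all scheduled visits except 8 and 9. It gives no duration and does not mention nicotine.

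**The concern.** Change from baseline in vital signs and EKG is a secondary endpoint. It can be read as a drug effect only if baseline and follow-up are measured under the same conditions. Here the baseline is abstinent by rule and the two late assessments are not. The study has one arm per dose level and no placebo group, so a shift caused by going back to coffee or cigarettes has nothing to be subtracted from. It would appear as late change after Careseng 1370.

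A related gap concerns attribution. Item 4 ends inside the DLT observation period, and the documents describe no record of alcohol, caffeine or nicotine intake after Day 7. An investigator judging a symptom on Days 8 to 10 may therefore lack the information needed to weigh another cause.

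**Working it through.** The check is a comparison of stated windows. The plan gives no figure of its own on this point to reproduce.

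**1. Condition at baseline.** Criterion 4 and item 4 both cover the 24 hours before Day 1. The Day 1 pre-dose vital signs and EKG are therefore taken after at least 24 hours without alcohol, caffeine or nicotine. If those data are missing, the fallback is Visit 1, where abstinence is not required.

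**2. Condition at follow-up.** With item 4 ending on Day 7:

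| Visit | Window | Days after item 4 ends |
|---|---|---|
| 10 | Day 10 to 14 | 10 − 7 = 3 to 14 − 7 = 7 |
| 11 | Day 20 to 24 | 20 − 7 = 13 to 24 − 7 = 17 |

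The visit lists in protocol section 7 add nothing on abstinence for either visit. After an early withdrawal, Visit 11 can fall before Day 7 and so under the restriction, so that visit may mix both conditions.

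**3. Which measurements are affected.** Vital signs and EKG are, because their baseline is Day 1 pre-dose. Laboratory tests are not affected in this way. None is scheduled at Day 1 pre-dose, their baseline is Visit 1, and neither that visit nor Visits 10 and 11 require abstinence.

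**4. Overlap with the DLT window.** If Day 7 is itself restricted, Days 8, 9 and 10 are not: 3/10 = 30%. If the restriction stops at the start of Day 7, four days are unrestricted: 4/10 = 40%. Visits 8 and 9 (Days 7 and 8) schedule no vital signs, EKG or laboratory tests, and only Day 10 of the Visit 10 window lies inside the DLT period. Exposure on Days 8 to 10 is therefore mainly through reported symptoms.

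**5. Record of intake.** Protocol section 3.5 requires recording of medications, supplements and herbal medicinal food. The minimum diary content in section 6.8 is sachets and dosing times. The diary is returned at Visit 8 and none is dispensed afterwards. SAP section 14.1.5 tabulates prohibited foods using CRF categories that the documents do not show, but after Day 7 these items are no longer prohibited.

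**6. Effect on the 3+3 rule (illustration only).** Let p be the chance per volunteer of a falsely attributed DLT. The documents give no value, so 2% to 5% is an assumption.

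- At least one such event in n volunteers: 1 − (1 − p)^n. For n = 3 this is 5.9% to 14.3%; for n = 6 it is 11.4% to 26.5%.
- Stopping a level needs two or more. From such events alone the probability is 1 − [(1 − p)³ + 3p(1 − p)² × (1 − p)³].
  - p = 2%: 1 − [0.9412 + 0.0576 × 0.9412] = 0.5%.
  - p = 5%: 1 − [0.8574 + 0.1354 × 0.8574] = 2.7%.

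The second calculation is the relevant one for escalation.

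**The case against.** **The affected analysis decides nothing.** The late vital-sign and EKG changes are summarised descriptively and have no decision rule. The same windows apply at every level, so comparison between levels is not biased by design. Both statements stand and they limit the weight of the point. They do not remove it: what is reported for each level is change from baseline, and the levels are small and not randomised, so habits may differ between them.

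**Fasting already helps.** It may limit same-morning caffeine or alcohol. It does not address nicotine or the day before, and its length is not stated.

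**Nothing requires item 4 to span the DLT window.** Correct. The Day 7 end is a gap in the design, not a contradiction, and it falls two days after the last dose. A DLT must also be Grade 2 or higher and judged at least possibly related, and the DSMB takes every escalation decision. On the other hand, the definition of a possible relation in protocol section 8.2 admits events to which other factors contributed, so such events are not automatically screened out.

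**Stronger readings to avoid.** A reader might infer that gamma-GT or triglyceride results suffer the same mismatch. They do not, because the laboratory baseline is Visit 1. A reader might also infer that one falsely attributed event overturns the escalation decision. Under protocol section 4, one DLT in 3 leads to expansion and one in 6 still allows escalation or completion; at the highest level, 0 of 3 is expanded anyway. The chance of at least one event, up to 26.5% in six volunteers, is therefore not the chance of a wrong dose decision, and it rests on an unsupported p.

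**Conclusion.** The point holds for vital signs and EKG at Visits 10 and 11. Their baseline is abstinent by rule, the follow-up is not, and without a control arm a late drug effect cannot be told apart from resumed alcohol, caffeine or nicotine. This follows from the stated windows and needs no assumed rate. It does assume that some volunteers are users who resume after Day 7; the documents neither exclude this nor say how many. The size of any shift cannot be derived from the documents.

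For Days 8 to 10 the documents support only a request for reconciliation. Three of ten DLT days (four on the narrower reading) are unrestricted and no reason is given. They do not support a claim of material distortion of the 3+3 decision: at an assumed p of 2% to 5%, such events alone would stop a level with probability of about 0.5% to 2.7%. Overall this is a modest improvement to the interpretability of a secondary endpoint.

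**What to change.** 1. Add to the instructions for Visits 10 and 11 in protocol section 7 and the schedule of assessments the same 24-hour abstinence from alcohol, caffeine and nicotine that applies before Day 1.
2. Record alcohol, caffeine and nicotine intake after Day 7, at least until the DLT window closes and before Visits 10 and 11, so that events on Days 8 to 10 can be assessed for other causes.
3. Ask the sponsor to reconcile the Day 7 end of item 4 with the Day 10 end of the DLT window, and to state whether Day 7 itself is restricted. The length of the restriction is for the sponsor to justify; none is proposed here.
4. For data already collected without this condition, footnote the SAP vital-sign and EKG tables to say that Visits 10 and 11 were not measured under the baseline condition.

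**Cost.** Protocol wording, a short intake question, and one day of abstinence before each of two visits. No procedure is added. One side effect: laboratory tests at Visits 10 and 11 would become abstinent values set against a Visit 1 baseline with no such requirement. The laboratory tests on Days 2 to 6 already have that feature, so the change creates no new kind of mismatch.
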